Inclusion Criteria

- 1. Patients referred for third molar removal from a primary care provider
- 2. Patients who volunteer participation
- 3. Patients may be either male or female
- 4. The patient has been screened by the primary investigator or supervising specialist for suitability to participate in the study
- 5. Are aged between 18 and 44 years
- 6. Are able to understand verbal and written instructions.
- 7. Present with bilateral similarly impacted mandibular third molars as determined using Winter's (1926) classification system , requiring surgical removal
- 8. Are able to tolerate outpatient oral surgery under local anaesthetic and intravenous sedation
- 9. ASA l or ll
- 10. The patient has provided informed consent regarding:
 - a. Participation in the study
 - i. The use of knotless sutures in the closure of the surgical wound
 - b. Surgical removal of third molars under local anaesthetic and intravenous sedation

Exclusion Criteria

- 1. American society of anaesthesiologists (ASA) physical classification¹ III or IV
- 2. Polypharmacy (\geq 5) medications²
- 3. \leq 17 years, \geq 45 years
- 4. Patients contraindicated to undergo surgical third molar removal
- 5. Opioid and illict drug addiction
- 6. Patients who have allergies or contraindications to the procedural usage of:

¹ Abouleish, A. E., Leib, M. L., & Cohen, N. H. (2015). ASA Provides Examples to Each ASA Physical Status Class. ASA Newsletter, 79(6), 38–49.

² Masnoon, N., Shakib, S., Kalisch-Ellett, L., & Caughey, G. E. (2017). What is polypharmacy? A systematic review of definitions. BMC geriatrics, 17(1), 230. https://doi.org/10.1186/s12877-017-0621-2

- a. midazolam
- b. dexamethasone
- c. parecoxib
- d. paracetamol
- e. ibuprofen
- f. co-amoxiclav
- g. cefazolin
- h. clindamycin
- i. chlorhexidine
- 7. The presence of symptomatic pericoronitis.
- 8. The presence of other pathology in the oral cavity.
- 9. Patients with poor oral hygiene (plaque >1/3 of tooth surface).
- 10. Pregnant or lactating women.
- 11. Patients unwilling to remove facial hair for the purpose of facial measurements in order to assess swelling.
- 12. Patients who are unable to give informed consent.
- 13. Patients who decline participation.
- 14. Patients who are unable to attend the required follow-up appointments.
- 15. Patients who are unable to comprehend directions and instructions.

Randomisation

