Local anaesthetic (lignocaine 2% with adrenaline 1:100 000) will be administered via an inferior dental block and buccal infiltration to the procedural sites prior to incision.

A two-sided flap design will be used, where the:

- 1. papilla distal to the first molar will be incised but not relieved,
- 2. the papilla distal to the second molar will be incised and relieved,
- 3. with a distal relieving incision across the external oblique ridge
 - a. In the event further exposure is required, an additional mesial relieving incision incorporating the distal papilla of the second molar will be made, making the flap 3-sided.

b. This will be determined pre-operatively, and where deviation from the planned flap design has occurred, this will be recorded.

The impacted third molar will be removed following any required sectioning of the tooth and bone removal.

The procedural site will be closed with simple interrupted 3-0 vicryl rapide sutures on the control side and the intervention side will be closed with a continuous running 3-0 v-loc suture. The difference in closure pattern is due to the differences in material handling and application.

A prescription for post-operative pain relief including 1g paracetamol, 400mg ibuprofen orally 4 times daily as needed, will be provided. Additional rescue analgesia will be prescribed, consisting of either 30mg codeine phosphate or 50mg of tramadol orally 4 times a day as needed. If required, the rescue analgesia will be recorded as part of the patient's post-operative pain diary. Patients who are unable to tolerate these medications will be excluded from this study.

Patients who require additional monitoring will be reviewed as per the institution's policy around post-operative complications.

Post-operative diary

The participants will be asked to rate the pain intensity as well as irritation from the sutures for the first 48 hours, every 6 hours while awake. A non-graduated visual analogue scale (VAS) will be provided to the patients for recording of this information as part of their pain diary.

The VAS will comprise of two 100mm horizontal lines with no markings along its length. The left end will be anchored with a vertical line and labelled 'no pain' and the right similarly anchored with a vertical line and labelled 'worst pain imaginable'. The score is determined by the distance between the end of the line on the left and the participant's mark.

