- 6. Participants will be asked to rate the pain and irritation experience at each side every 6 hours while awake for the first 48 hours. A non-graduated 100mm VAS, in the patient's post-operative diary will be included, for every waking 6 hour interval.
 - i. They will additionally record under the respective pages:
 - i. The time between the end of the procedure (will be written down into the booklet at the conclusion of the procedure) and the first use of rescue medication
 - ii. The amount of rescue analgesia consumed each day
 - iii. Any adverse events experienced post-operatively (e.g. vomiting, nausea, headaches, uncontrolled pain and swelling from the site)
- 7. Participants will be asked to attend a post-operative review with the primary investigator at 48h following their procedure, and again at 7 days.
 - i. A repeat triplicate of facial swelling measurements will be taken at each of these appointments.
 - ii. A post-operative questionnaire will be completed at each appointment. This contains items relating to post-operative pain, irritation at the sites, whether they needed to be reviewed in a community-based practice or at the institution in the intervening period, whether intervention was required, compliance with the prescribed pain relief, requirement for rescue analgesia, OHIP-14, Locker's global oral health measure. Additionally, the patient's perception of which side they felt was healing better will be recorded.

Measurement of facial swelling

Facial swelling will be determined by tape measurements between the tragus and soft tissue pogonion (A), tragus and lateral corner of the mouth (B), lateral corner of the eye and the angle of the mandible (C). Facial measurements will be calculated as: (A

+B+C)/3, and facial swelling (%) will be calculated as: [(postoperative measurement – preoperative measurement] × 100% (Baqain et al., 2012).

- 1. These measurements will be taken prior to commencement on the day of the procedure;
- 2. 48h post-operatively;
- 3. 7 days post-operatively.

Data entry

Data will be entered into a Microsoft Excel spreadsheet, recording the triplicate of facial measurements, the nature of impaction involved, the time taken to close the surgical site, the intervention side/site and scores from the operative questionnaires. The data will be checked for errors prior to de-identification and data analysis.

Statistical considerations and data analysis

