Sample size. Power analysis yielded a sample size of 63 participants based on a paired sample t-test analysis with alpha of 0.01, power of 0.9, and a moderate effect size (Cohen's d = 0.5). Previous research supports that moderate to large effect sizes can be expected for our key outcome, closure time (Durand, 2017; Zhu et al., 2017). Furthermore, a simulation study on the sample considerations of split mouth designs also indicated that a sample size of approximately 60 participants would be appropriate. 70 participants will be recruited to account for possible drop-out and data loss from participant protocol deviation.

Statistical approach. Statistical analyses will be conducted using the statistical programming language R. Our outcome variables, closure time, inflammation, and pain, will be modelled using separate mixed models Analyses of Variance (ANOVA) with suture type as a within-subjects variable and age, sex, ethnicity, smoking status, previous pericoronitis and dental anxiety score as between-subjects variables. In the case of inflammation, irritation and pain, we will use a repeated measures design to account for multiple follow-ups. A post-hoc polynomial comparison of follow-up outcomes by suture type will also be used to determine whether the trajectory of healing differed significantly between suture types. In all cases, we will use an alpha

of 0.01, more stringent than the traditional 0.05. Using a lower alpha allows us to be more certain of our findings and also implicitly controls for the multiple comparisons we are making across different outcome variables.

Bias and confounding

Bias

The patient is blinded to which side receives the intervention to minimise reporting bias. Handedness will be controlled for by allocating an equal number of interventions to each of the left and right sides through the randomly selected system of sealed envelopes drawn prior to the procedure. Uneven loss to follow-up or withdrawal may cause one intervention-control-side combination to be over-represented.

Modifiers

Age

Increasing age has been associated with increased procedural difficulty. We have excluded individuals 45 years or older to minimise the effect of age.

Peri-operative medications

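### The planned flap may differ between a patient's two sides and is neither recorded as such nor adjusted for, which adds avoidable noise to the paired closure-time comparison

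*Protocol*

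**What the plan says.** - **Flap (Study procedure, Surgical procedure, item 3).** The standard flap is two-sided. If further exposure is required, "an additional mesial relieving incision incorporating the distal papilla of the second molar will be made, making the flap 3-sided". Item 3b adds: "This will be determined pre-operatively, and where deviation from the planned flap design has occurred, this will be recorded".
- **Matching of sides (Inclusion Criteria, item 7).** Patients must "Present with bilateral similarly impacted mandibular third molars as determined using Winter's (1926) classification system". No inclusion or exclusion criterion mentions the flap.
- **Outcome (Data collection, item 5).** Closure time runs from the first bite of soft tissue until the wound edges are satisfactorily approximated. It is a raw time, not scaled to incision length.
- **Data entry.** Besides the facial measurements, the list names "the nature of impaction involved, the time taken to close the surgical site, the intervention side/site and scores from the operative questionnaires". Flap type is not on it.
- **Analysis (Statistical approach).** Suture type is the within-subjects factor. The other named terms are age, sex, ethnicity, smoking status, previous pericoronitis and dental anxiety score, all between-subjects.
- **Sample size.** It rests on a "paired sample t-test analysis with alpha of 0.01, power of 0.9, and a moderate effect size (Cohen's d = 0.5"), and the text expects "moderate to large effect sizes can be expected for our key outcome, closure time".
- **Allocation (Randomisation; Data collection, item 5).** The side for the intervention is drawn from sealed envelopes before the procedure, with equal numbers to left and right.

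**The concern.** A three-sided flap has one more incision limb than a two-sided one, so it can be expected to take longer to close with either suture. In a patient whose flaps differ, the closure-time difference is then the suture effect plus or minus the time for the extra limb.

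Nothing named in the plan removes that component. Matching on impaction class constrains tooth orientation, not the incision. A patient planned with different flaps has not deviated from plan, so item 3b does not require the difference to be captured. A covariate that takes the same value on both sides of one mouth cannot explain a difference between those sides.

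At stake is precision on the outcome for which the trial was sized. A second, smaller matter is timing. The flap is decided pre-operatively and the envelope is drawn before the procedure, but the order of the two is not stated. One operator plans, cuts and sutures, so a flap planned after the envelope is opened could in principle depend on the allocation.

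**Working it through.** **1. The plan's own figure.** The protocol states: "Power analysis yielded a sample size of 63 participants based on a paired sample t-test analysis". Inputs from that section: alpha 0.01, power 0.9, d = 0.5 in SDs of the paired difference. Sidedness is not stated and is taken as two-sided. With the noncentral t distribution (n − 1 degrees of freedom, noncentrality d√n), the smallest n reaching 0.90 is 63, with power 0.9007. The one-sided version gives 55, so the two-sided reading is the one that reproduces the plan. Recruiting 70 matches 63 / 0.90 = 70, an implied loss of about 10%. These figures stand.

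**2. Effect of discordant flaps.** Let σ be the SD of the paired difference among patients with the same flap on both sides, p the share of patients whose planned flaps differ, and k the extra closing time for the third side in units of σ. Side is randomised, so in a discordant patient the extra time adds +kσ or −kσ with equal probability. That term has mean 0 and variance p·k²·σ². Hence

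- variance of the paired difference = σ²(1 + p·k²)
- effective d = 0.5 / √(1 + p·k²)

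The protocol gives neither p nor k. The ranges below (p from 5% to 20%, k from 0.5 to 1.5) are assumptions.

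| p | k | 1 + p·k² | effective d | power, n = 63 | power, n = 70 | n for 0.90 |
|---|---|---|---|---|---|---|
| 0 | – | 1 | 0.500 | 0.901 | 0.934 | 63 |
| 0.05 | 0.5 | 1.0125 | 0.497 | 0.897 | 0.931 | 64 |
| 0.10 | 0.5 | 1.025 | 0.494 | 0.892 | 0.927 | 65 |
| 0.10 | 1 | 1.10 | 0.477 | 0.866 | 0.906 | 69 |
| 0.20 | 1 | 1.20 | 0.456 | 0.829 | 0.875 | 75 |
| 0.20 | 1.5 | 1.45 | 0.415 | 0.736 | 0.792 | 90 |

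Worked line: p = 0.20, k = 1 gives 1 + 0.20 × 1² = 1.20, and 0.5 / √1.20 = 0.456. The n = 70 column assumes no losses.

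**3. Bias or noise?** The added term has mean 0 under randomisation of side. As a check, 40,000 simulated trials of 63 patients with no suture effect, at each of three settings, gave rejection rates against a nominal 0.01 of 0.0093 (p = 0.1, k = 1), 0.0099 (p = 0.2, k = 2) and 0.0092 (p = 0.3, k = 2). The test keeps its level, and the cost is power alone.

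**4. What a side-level term does.** Regress the paired difference on the between-side difference in planned flap (−1, 0 or +1). If the extra time is additive and similar for both sutures, this removes the p·k² component and returns the residual variance to σ², for one degree of freedom. None of the six patient-level covariates can take that role, since each is constant within a patient.

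**The case against.** **Discordance should be uncommon.** The two-sided flap is the default, the third side is added only when exposure demands it, and the teeth must be similarly impacted. This stands as a reason to expect a small p. It does not make p zero, because two teeth in the same Winter class can still need different exposure.

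**The size is assumed.** Neither p nor k is in the protocol, and at small values the loss is negligible (0.892 to 0.897 at n = 63). The calculation also takes d = 0.5 to describe concordant pairs. The text speaks only of "a moderate effect size (Cohen's d = 0.5"), a conventional value that may already cover all between-side variation, and it is the low end of the effects expected. All of this stands and limits the point to a modest improvement.

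**The data may exist anyway.** A deviation can be identified only if the plan is known, and the data-entry list also leaves out age, sex, ethnicity and smoking status, which the model needs. So the list is not exhaustive, and a reader who inferred from it that flap type could never be recovered would go further than the text allows. The protocol also promises in general terms to address confounders by modelling, and an analysis plan not shown could add a flap term. What remains is that this protocol does not provide for per-side recording of the planned flap and names no side-level covariate.

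**Chance imbalance.** A reader might infer that a chance excess of three-sided flaps under one suture would be mistaken for a suture effect. The documents do not support this: such imbalance is part of the variance of the paired difference and is covered by alpha, as step 3 shows.

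**Conclusion.** The point holds as a matter of precision. A planned difference in flap between sides is allowed, is not a deviation, and would enter the paired closure-time difference unadjusted by any named term. With the side randomised, and the flap planned independently of the allocation, it adds variance and no expected bias. Power at 63 participants would fall from 0.90 to anywhere between about 0.90 and 0.74 over the assumed ranges. The low figure needs both 20% discordance and an extra time of 1.5 SD. The loss applies only if d = 0.5 does not already include this variation, and it is smaller if all 70 participants are analysed.

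Two stronger readings are not supported. The stated sample size is not wrong: it reproduces exactly. Nor do the documents show a biased comparison. The unstated order of flap planning and envelope opening leaves open a route by which allocation could influence the flap, but nothing suggests that this is intended or expected.

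Nor is there a case for restricting eligibility to patients with the same planned flap on both sides. That would trade recruitment against a variance of unknown size, when adjustment achieves the same purpose without excluding anyone.

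**What to change.** 1. State that the planned flap for each side is written down before the allocation envelope is opened.
2. Record the planned and the actual flap (two- or three-sided) for each side in the study dataset, whether or not there was a deviation.
3. Include planned flap as a side-level covariate in the closure-time model. Use the planned flap, because once its plan is fixed before the envelope is opened the allocation cannot have influenced it; the actual flap may be changed by an operator who knows the allocation.
4. Pre-specify a sensitivity analysis limited to patients with the same planned flap on both sides.

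The cost is one data field per side for the plan, a matching entry for the flap used, and one model degree of freedom. Nobody is excluded, the sample size need not change, and the clinical choice of flap is left as it is.

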This will be compared against baseline measures collected prior to the procedure, allowing for assessment and analysis.

Informed consent

Patients who are deemed suitable at the participation will be invited following the initial consultation process. Information will be delivered verbally and patients will be given a written copy of this, outlining:

- The nature and purpose of the study;
- Participant responsibility; and
- The right to withdraw.

Patients will be given ample opportunity to raise any questions or concerns prior to enrolment. Following enrolment, further clarifications can be sought at any time. Contact details will be provided to the patients for them to communicate any questions or concerns.

Patients will be able to withdraw consent at any time and will not be coerced to do otherwise. A signed form documenting their participation in the study will be separate from their consent to proceed with surgical third molar removal. Patients will be able to withdraw from the study, and continue to receive the required treatment without prejudice.

Participants will be required to present for their surgery on the scheduled date and time. Furthermore, participants will be required to complete their pain diary and attend the scheduled post-operative review appointments at 48h and 7 days. They will be required to record their perceived post-operative pain and irritation on each side of the mouth on the 100mm VAS in the post-operative diary provided every 6 hours while awake, for the first 48 hours post-operatively. The use of rescue analgesia, and any interim presentations to a healthcare provider regarding pain or discomfort, should be recorded. This diary should be returned to the principal investigator at the 48h post-operative appointment.

Participant incentive

The treatment fees will be in line with the institution's fee schedule and no monetary incentives will be provided to encourage patients to participate. Patients will be provided with the same standard of care regardless of participation status.

Data collection

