- 1. Eligible patients will be invited to participate and will be provided with a copy of the participant information sheet if they express interest. The initial appointment will involve a consultation with the clinician/primary investigator. If the patient provides informed consent to participate, they will then complete the pre-operative questionnaire. This questionnaire contains the Oral Health Impact Profile, OHIP-14 (Slade, 1997), Locker's Global Oral Health Item (Thomson et al., 2012), and the Dental Anxiety Scale (Corah, 1969).
- 2. Patients will be assigned a study participant number which will be used during data collection. This will be recorded separately from their clinical records. According to the applicable institutional protocol, the intervention site, material and batch number will be recorded in the patient's clinical record.
- 3. The type of third molar impaction according to the Winter's classification (mesio-angular, disto-angular, vertical, horizontal, transverse bucco-lingual, inverted) will be recorded for each participant. Clinically and radiographically similar impaction patterns are crucial in a split-mouth design.
- 4. Prior to the procedure, the patient will:
 - i. Complete a VAS score on pre-operative pain and irritation;
 - ii. Have a triplicate of baseline measurements to later aid in assessing facial swelling will be recorded.
 - iii. Have their height and weight taken.

The removal of the bilateral similarly impacted third molars will then commence under IV sedation.

5. The time taken for removal of the mandibular third molar from each side will be recorded, starting from the time of the initial incision to the completion of tooth removal. Both sites will be irrigated and inspected to remove and fine debris in the surgical site, ensure no remnants remain and there is no inadvertent damage to adjacent structures. The time taken for wound closure will also be recorded, starting from the time of the first bite of the soft tissue, to the time the sutures have been placed and the wound edges satisfactorily approximated.

- i. Prior to the procedure, the side receiving the intervention will be drawn.
- ii. This will be drawn at random, with the nurse and the clinician unaware of which side the intervention is assigned to until the envelope is opened.

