Van Rijssel, E. J. C., Brand, R., Admiraal, C., Smit, I., & Trimbos, J. B. (1989). Tissue Reaction and Surgical Knots: The Effect of Suture Size, Knot Configuration, and Knot Volume. Obstetrics & Gynecology, 74(1), 64–68.

Appendices

Appendix 1

Facial measurements before wisdom tooth removal

Date: _____

*Time:*_____

[figure not shown]
Right facial measurements

Right factar measurements				
	(A) tragus and soft tissue pogonion	(B) tragus and lateral corner of the mouth	(C) lateral corner of the eye and the angle of the mandible	
B				

Left facial measurements

(A) tragus and soft tissue pogonion	(B) tragus and lateral corner of the mouth	(C) lateral corner of the eye and the angle of the mandible

Appendix 2

Facial measurements 2-days following wisdom tooth removal

Date: _____

*Time:*_____

[figure not shown]
Right facial measurements

Right factal measurements				
	(A) tragus and soft	(B) tragus and lateral	(C) lateral corner of	
	tissue pogonion	corner of the mouth	the eye and the angle	
			of the mandible	
$ \rangle$				

Left facial measurements

	(A) tragus and soft	(B) tragus and lateral	(C) lateral corner of
	tissue pogonion	corner of the mouth	the eye and the angle of the mandible
C			

Appendix 3

Facial measurements 14-days following wisdom tooth removal

Date: _____

Time: _____

Right facial measurements

(A) tragus and soft	(B) tragus and lateral	(C) lateral corner of		
tissue pogonion	corner of the mouth	the eye and the angle		
		of the mandible		

Left facial measurements

	(A) tragus and soft tissue pogonion	(B) tragus and lateral corner of the mouth	(C) lateral corner of the eye and the angle of the mandible
A C

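### The pre-operative pain and irritation VAS is not specified per side, so on its plain reading it cannot adjust the within-patient suture comparison (minor)

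*Protocol*

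**What the plan says.** Pain and irritation are listed under the primary objectives. After surgery both are side-specific. Data collection item 6 states: "Participants will be asked to rate the pain and irritation experience at each side every 6 hours while awake for the first 48 hours". The Informed consent section likewise has participants "record their perceived post-operative pain and irritation on each side of the mouth on the 100mm VAS".

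The Post-operative diary section ends by saying of these ratings: "This will be compared against baseline measures collected prior to the procedure, allowing for assessment and analysis". The only description of that baseline is in Data collection item 4.i, where the patient is to "Complete a VAS score on pre-operative pain and irritation". No side is given.

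The diary instrument is described as follows: "The VAS will comprise of two 100mm horizontal lines with no markings along its length". The text does not say whether the two lines stand for left and right or for pain and irritation, and it does not extend this layout to the pre-operative score.

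For swelling, the pre-operative form in Appendix 1 has separate tables for the right side and for "Left facial measurements".

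The Statistical approach paragraph models "suture type as a within-subjects variable and age, sex, ethnicity, smoking status, previous pericoronitis and dental anxiety score as between-subjects variables". It names no baseline VAS term.

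**The concern.** The trial asks about a difference between two sides of the same mouth. A baseline helps that comparison only if it can differ between the sides. A single score per patient is a patient-level quantity, and the split-mouth design already removes patient-level quantities.

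Soreness on one side before surgery is a site-level factor. Sides are matched on impaction pattern, not on symptoms, and the planned covariates are all patient-level. Randomising the side balances such soreness on average, but in any one trial a chance imbalance can remain. With an unsided baseline that imbalance cannot be adjusted for, and a reported change from baseline for a given side would have no clear meaning when the two sides started at different levels.

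This is a matter of data collection. A later analysis plan can decide how to use a baseline, but it cannot recover a side-specific score that was never taken.

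**Working it through.** **1. The plan's own figure.** Sample size paragraph: paired t-test, alpha 0.01, power 0.9, d = 0.5, n = 63. The noncentral t calculation, two-sided, gives n = 62.87, rounded up to 63, with power 0.901 at 63. The figure reproduces. The key outcome named there is closure time, so nothing below changes it.

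**2. A shared baseline cancels.** Let K and C be the post-operative scores on the knotless and conventional sides, and B one baseline for the patient.

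(K − B) − (C − B) = K − C, for any B.

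Assumed example in mm: baseline left 30, right 0; post-operative left 50, right 40.
- Shared B of 0, 15 or 30: left-minus-right contrast is 10 each time, the same as the raw scores.
- Per-side baselines: changes are 50 − 30 = 20 and 40 − 0 = 40, contrast −20.

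The example shows only that the two calculations carry different information. It does not show that −20 is the right answer and 10 the wrong one (step 3).

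With a shared B, a side's change differs from its own change by (that side's baseline − B). This cannot be zero on both sides when the sides differ.

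**3. Bias.** Assume a mean left-minus-right baseline difference of 10 mm, SD 20 mm, with side randomised in 63 patients split 31/32. The expected imbalance between sutures is 10 × (31 − 32)/63 = −0.16 mm. Simulation gave −0.18 mm. This is zero apart from the odd number of patients. The chance imbalance in a single trial has SD 20/√63 = 2.5 mm. The raw post-operative contrast is therefore unbiased, and what an adjustment could recover is precision.

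**4. Size of the precision gain.** Let r be the correlation between the baseline and post-operative side differences. The documents give no value, so a range is assumed. Scale the post-operative side difference to SD 1, and give the baseline side difference the same SD.
- Raw scores or shared baseline: variance 1.
- Per-side baseline as covariate: variance 1 − r².
- Simple per-side change: variance 2 − 2r.

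Power at n = 63, two-sided alpha 0.01, d = 0.5 on the raw difference (effective d is 0.5 divided by the SD, before the cost of the extra parameter):

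| r | Variance cut, covariate | Raw or shared | Covariate | Simple change |
|---|---|---|---|---|
| 0 | 0% | 0.90 | 0.90 | 0.56 |
| 0.2 | 1 − 0.96 = 4% | 0.90 | 0.91 (d = 0.5/√0.96 = 0.510) | 0.68 (d = 0.5/√1.6 = 0.395) |
| 0.3 | 1 − 0.91 = 9% | 0.90 | 0.93 | 0.75 |
| 0.5 | 1 − 0.75 = 25% | 0.90 | 0.97 | 0.90 |

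At a smaller assumed effect, d = 0.4, simulation including the extra parameter gave power of about 0.70 unadjusted, and 0.71, 0.73 and 0.83 adjusted at r = 0.2, 0.3 and 0.5. At r = 0 the extra parameter costs about 0.01.

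**5. Why a change score is not the remedy.** With equal SDs, 2 − 2r exceeds 1 whenever r < 0.5, so subtracting the per-side baseline then loses power against doing nothing. The covariate form does not have this problem. The break-even of 0.5 rests on the equal-SD assumption.

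**The case against.** The strongest reply is that one score per patient is inferred from an article and from silence. Item 4.i uses the singular for two symptoms at once. Item 4.ii, on facial measurements, also omits the side, yet Appendix 1 collects them per side. Item 6 uses the singular for an instrument known to be rated per side. The pre-operative VAS form is not shown and may have a line for each side. This stands: the unsided reading is the plain one but not certain. If the form is already per side, the remedy shrinks to a clarifying sentence and the model term.

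A reader might infer that the protocol subtracts a single baseline from both sides and so gets the suture comparison wrong. The documents do not support this. For swelling they write a postoperative-minus-preoperative formula; for the VAS they write none and say only that scores will be compared with baseline. The raw post-operative contrast is valid because side is allocated at random, with equal numbers to each side.

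The gain may also be slight. Symptomatic pericoronitis and other oral pathology are exclusions, so many baselines may sit near zero. The gain from 0.70 to 0.71 at r = 0.2 is within simulation error. The diary asks about irritation caused by the sutures, which has no clear counterpart before surgery, so the point concerns pain more than irritation. All of this stands and limits the severity. It does not remove the point that an unsided baseline cannot serve a within-patient comparison.

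**Conclusion.** The point holds as a minor, cheap improvement. If item 4.i is carried out as it plainly reads, the baseline VAS contributes nothing to the suture contrast, and change from baseline on each side is not interpretable when the sides differ. The estimated suture effect is not biased. The precision forgone is 4% to 25% of the variance over the assumed r of 0.2 to 0.5, probably near the lower figure, and applies mainly to pain. This rests on the unsided reading of item 4.i and on an assumed r, since the documents give no side-to-side baseline data.

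**What to change.** Reword Data collection item 4.i so that pre-operative VAS scores are recorded separately for the left and the right side, for pain and for irritation, and state in the diary description which line belongs to which side and symptom.

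In the pain model, enter the side-specific baseline as a within-patient covariate (equivalently, adjust the suture contrast for the baseline side difference). Do the same for irritation only if the team judges a pre-operative irritation score meaningful. Do not analyse a simple per-side change score.

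Cost: two extra VAS marks per patient, a sentence of protocol text, one model term and one degree of freedom, worth about 0.01 of power if baseline proves unrelated to outcome. No visit or procedure is added, and the sample size stays at 63, with 70 recruited.
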